20.0 Withdrawal of Subjects

- N/A: This study is not enrolling subjects. This section does not apply.

20.1 Describe **anticipated** circumstances under which subjects may be withdrawn from the research without their consent.

Response:

Lack of compliance with oral hygiene, post-operative instructions, or follow-up appointments. Also, if any changes occurred in the medical history or medications taken that might affect the treatment, healing, or outcomes e.g. some blood pressure or epilepsy medications, pregnancy, antibiotics, diabetes, smoking. Lastly, if any other oral condition occurred on the teeth of interest e.g. cavity, root canal, loosening of the teeth or pockets. All subjects will be informed of any new information that may affect their health, welfare, or choice to stay in the research.

20.2 Describe any procedures for orderly termination.

NOTE: Examples may include return of study drug, exit interview with clinician. Include whether additional follow up is recommended for safety reasons for physical or emotional health.

Response:

At the end of the study, the patients will be given a report of the study and the results, and they will be informed if any further procedure is needed for the site maintenance and the future recommendations will be explained.

20.3 Describe procedures that will be followed when subjects withdraw from the research, including retention of already collected data, and partial withdrawal from procedures with continued data collection, as applicable.

Response:

Upon withdrawal from the study before the one-month follow-up after the surgery, all measurements and data collected will be discarded and will not be used in any research publication. If withdrawal occurred after the 6 weeks follow-up, the patient will be asked if they would agree on using their data in the study analysis and publication. If they agreed, data will be retained, and if not will be discarded.

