Clinical measurements will be collected during the study visit at 6 weeks, 3, 6, 12, 18, and 24 months post-surgical treatment, healing and patient's condition will be assessed at day 1 and 2 weeks post-surgically. The medical monitor will assure patient's safety is maintained upon evaluation of all measurements. If patients developed any treatment complications, they will be informed and treated accordingly.

19.5 Describe the frequency of safety data collection.

Response:

All outcomes will be recorded at 6 weeks, 3, 6, 12, 18, and 24 months after the surgery. Healing index and patient's condition checklist at day 1 and 2 weeks post-surgically, and pain index the first 3 weeks after the surgery. Surgical time for each surgical procedure and suturing time for CTG will be calculated at the surgical visit.

19.6 Describe who will review the safety data.

Response:

Medical monitor is assigned by the organization sponsor to review the data periodically and make sure all patients are still eligible for treatment and that all the study criteria are met. The medical monitor is a certified dentist who is not involved in the patient treatment.

19.7 Describe the frequency or periodicity of review of cumulative safety data.

Response:

Monthly.

19.8 Describe the statistical tests for analyzing the safety data to determine whether harm is occurring.

Response:

Pre and post comparison through paired t-test of the measurements

19.9 Describe any conditions that trigger an immediate suspension of the research.

Response:

Developing diabetes, pregnancy, periodontal disease, immune deficiency, smoking, uncontrolled medical condition, or persistent non-compliance with study

appointments, instructions or oral hygiene instructions will result in immediate suspension from the study.

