21.0 Risks to Subjects

21.1 List the reasonably foreseeable risks, discomforts, hazards, or inconveniences to the subjects related to their participation in the research. Consider physical, psychological, social, legal, and economic risks. Include a description of the probability, magnitude, duration, and reversibility of the risks.

NOTE: Breach of confidentiality is always a risk for identifiable subject data.

Response:

Some forms of gingival recession will benefit from soft tissue graft procedure and will be recommended to be done for the subjects whether they are in a study or not as standard of care. All soft tissue grafting surgeries might possess the same surgical risks including; pain, discomfort, bleeding, failure and redo of procedure, swelling, bruising, infection, tooth sensitivity, temporary or permanent numbness in surgical area, inflammation.

Risks related to the anesthetics might include but are not limited to allergic reactions, accidental swallowing of foreign matter, facial swelling or bruising, pain, soreness or discoloration at the site of injection of the anesthetics.

Finally, Breach of confidentiality is always a risk for identifiable subject data.

21.2 Describe procedures performed to lessen the probability or magnitude of risks, including procedures being performed to monitor subjects for safety.

Response:

Review of medical history and medications of the patient, patients will be instructed to use over the counter pain medications including ibuprofen and/or acetaminophen as needed. Also, maintenance of good oral hygiene will decrease the chance of infection or inflammation of the surgical site. Day one and 2 weeks follow-up will be performed and a patient's condition checklist will be followed. Also, the patients will record their pain throughout the first 3 weeks after the surgery.

*21.3 If applicable, indicate **which procedures** may have risks to the subjects that are currently unforeseeable.*

Response:

All soft tissue surgeries will have similar risks whether in the study or outside the study.

21.4 If applicable, indicate which research procedures may have risks to an embryo or fetus should the subject be or become pregnant.

Response:

Upon pregnancy the subject will be withdrawn from the study.

21.5 If applicable, describe risks to others who are not subjects.

Response:

None

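### Section 20.3 discards all data of subjects withdrawn before an unscheduled one-month point, so early pain, healing and complication data can be lost according to outcome

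*Protocol*

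**What the plan says.** **Data after withdrawal (Protocol 20.3).** "Upon withdrawal from the study before the one-month follow-up after the surgery, all measurements and data collected will be discarded", and they may not be published. Neither safety data nor the reason for leaving is an exception. Later on, the rule changes: "If withdrawal occurred after the 6 weeks follow-up, the patient will be asked if they would agree on using their data in the study analysis". If the subject refuses, the data are discarded.

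**Who may be removed.** Section 20.1 lists circumstances for withdrawal without the subject's consent. One is a change in medical history or medication that might affect treatment, healing or outcome: "some blood pressure or epilepsy medications, pregnancy, antibiotics, diabetes, smoking". Another is "if any other oral condition occurred on the teeth of interest e.g. cavity, root canal, loosening of the teeth or pockets". Section 19.9 is firmer and prescribes immediate suspension from the study for a list that begins "Developing diabetes, pregnancy, periodontal disease, immune deficiency, smoking, uncontrolled medical condition, or persistent non-compliance with study".

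**Surgical risks (21.1).** The foreseeable risks of any soft tissue graft include "pain, discomfort, bleeding, failure and redo of procedure, swelling, bruising, infection, tooth sensitivity".

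**Endpoints and timing.** Section 2.1 lists the Pain Index and Healing Index as primary endpoints beside root coverage, with probing depth and attachment level as secondary. Section 17.1 narrows the primary endpoint to recession depth. Under 10.1 and 19.5, pain is recorded for 3 weeks after surgery, and the healing index and patient's condition checklist at day 1 and 2 weeks. Recession depth and the other clinical measurements are taken at baseline and then from 6 weeks. The second surgery follows 3 weeks after the first (10.1).

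**The concern.** Removal from the study can depend on how the surgery went, and removal in the first month deletes the record of it. Antibiotics might be given for an infected site. Root canal treatment, loosening or pockets on an operated tooth, or periodontal disease, might also follow surgery. No section separates events arising from the study procedures from unrelated ones.

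At stake are the early tolerability outcomes on which the two techniques are expected to differ, and the complication record. The hypothesis in 1.2 is that the pinhole technique (PST) is not inferior to the connective tissue graft (CTG). Losing subjects who did badly on the PST side favours that hypothesis, and losing those who did badly on the CTG side works against it. Once data are discarded, no statistical analysis plan can recover them.

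**Working it through.** **1. The plan's own sample size.** Inputs from 17.1: SDs 0.91 and 0.95, correlation 0.46, difference 0.4 mm, two-sided 0.05, power 80%.

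- SD of the paired difference = √(0.91² + 0.95² − 2 × 0.46 × 0.91 × 0.95) = √0.935 = 0.967 mm.
- Normal approximation: ((1.960 + 0.842) × 0.967 / 0.4)² = 45.9, so 46 pairs.
- Paired t-test (noncentral t): 48 pairs, with power 80.1% (79.3% at 47).
- 48 + 4 dropouts = 52, an allowance of 4/52 = 7.7%.

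The stated 48 and 52 reproduce. The allowance covers lost numbers only, not selective loss.

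**2. What lies inside the discard window, counted from one surgery.**

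| Data | Collected | Before one month? |
|---|---|---|
| Healing index | day 1, 2 weeks | yes, all |
| Condition checklist (bleeding, infection, swelling) | day 1, 2 weeks | yes, all |
| Pain diary and pain medication | daily for 3 weeks | yes, all |
| Post-operative recession depth | from 6 weeks | no |
| Post-operative probing depth, attachment level | from 6 weeks | no |

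**3. The clock.** The scheduled visits go from 2 weeks to 6 weeks, so the one-month follow-up is not among them. Withdrawals between one month and 6 weeks fall under neither rule. The choice of surgery matters. Taking a month as 30 days (an assumption) and the surgeries 21 days apart:

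- From the first surgery, the window closes 30 − 21 = 9 days after the second, before that procedure's 2-week visit.
- From the second surgery, it closes 21 + 30 = 51 days after the first. The first site's 6-week value (day 42) could then be discarded, but its partner site has no post-operative value yet, so no paired difference is deleted.

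**4. Triggers against risks.** Infection is a named risk in 21.1, and antibiotics are a trigger in 20.1. Procedure failure is a named risk, and loosening or pockets on the study teeth are triggers. Probing depth is an endpoint, and pockets are a reason for removal. None of 19.9, 20.1 or 20.3 says how an event that may come from the surgery is handled.

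**5. Size, under assumed values.** Suppose k of 52 subjects have a PST result x mm worse than their CTG result and are lost, and the rest average no difference. The mean over all 52 then differs from the reported mean by k × x / 52.

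| k | x (mm) | Shift (mm) | Share of 0.4 mm |
|---|---|---|---|
| 2 | 2 | 0.08 | 19% |
| 4 | 1 | 0.08 | 19% |
| 4 | 2 | 0.15 | 38% |
| 4 | 3 | 0.23 | 58% |

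For safety, if 4 of 52 (7.7%) have an early complication, are withdrawn and have their data discarded, the report shows 0/48. Its two-sided 95% upper limit is 1 − 0.025^(1/48) = 7.4%, below the 7.7% that occurred.

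Only the 4 and the 52 come from the plan. The reasons for loss, the values of x and the complication count are assumptions.

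**The case against.** Several points on the other side stand.

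- **Discretion.** Section 20.1 answers when subjects may be withdrawn, so removal there is not automatic. Its triggers often have causes unrelated to surgery, and complications have their own path: the checklist records infection with its probable cause, and section 19 provides for evaluation and treatment. A reader might infer that a treated site infection must lead to withdrawal and deletion. No section says so, but none excludes it, and discretion used after the outcome is known does not remove the selection.
- **Efficacy.** A reader might infer that the worst root-coverage results are deleted. Counted from a given surgery, no post-operative recession depth exists before 6 weeks, and later values stay if the subject agrees. Pockets would ordinarily be found at scheduled probing from 6 weeks, when the agreement rule applies. Keeping earlier data would therefore restore no power for recession depth.
- **Design.** Someone who leaves before the second surgery has no PST–CTG pair under any retention rule. The order is randomised, so order alone favours neither technique. Bias needs complication or quitting rates that differ between techniques.
- **Protection of subjects.** One might argue that withdrawal protects nobody because the surgery is already done. That fails: until week 3 a second operation is pending.
- **Unseen analysis plan.** Analysis sets and sensitivity analyses may be defined there. That does not answer a protocol instruction to discard the data.

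**Conclusion.** The point holds for early pain, healing and complication data. Followed as written, 20.3 removes all of these for anyone withdrawn in the first month, and the removal triggers are not separated from consequences of the surgery. The rule also cannot be applied consistently: its visit is not scheduled, it leaves a gap up to 6 weeks, and the surgery is not named.

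For recession depth the claim is narrower: follow-up ends, and the subject can veto use of later data. The shift of 0.08 to 0.23 mm with 4 subjects lost, and the change from 4/52 to 0/48, show scale under assumed values and are not forecasts. The direction depends on which technique caused the losses, and the documents give no reason for the 4 expected dropouts.

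This should be corrected now: 17.1 reports 28 cases already treated, and discarded records may be unrecoverable.

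**What to change.** Amend the protocol, with matching consent wording:

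1. **20.3, retention.** Keep, analyse and report all data collected up to withdrawal, including every complication whatever the withdrawal date.
2. **Continued observation.** After a 20.1 or 19.9 event, continue outcome and safety observation unless the subject withdraws consent. Whether the second surgery goes ahead remains a clinical decision outside this point.
3. **Timing.** Replace the one-month point by a scheduled visit, name the surgery from which time is counted, and close the gap before 6 weeks.
4. **Reconciliation.** Bring 19.9, 20.1 and 21.1 into agreement on events that may arise from the study surgery.

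Lost pairs should not be filled in as no reduction at both sites. That sets each pair's difference to zero: with 4 such pairs, a true 0.4 mm becomes 48 × 0.4 / 52 = 0.37 mm, a pull towards no difference that favours the non-inferiority hypothesis.

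The cost is protocol and consent wording plus continued visits for some subjects. The planned 48 and 52 are unchanged. The downside is that some retained subjects will have had antibiotics or new dental conditions, which a per-protocol sensitivity analysis can address.

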21.0 Risks to Subjects

21.1 List the reasonably foreseeable risks, discomforts, hazards, or inconveniences to the subjects related to their participation in the research. Consider physical, psychological, social, legal, and economic risks. Include a description of the probability, magnitude, duration, and reversibility of the risks.

NOTE: Breach of confidentiality is always a risk for identifiable subject data.

Response:

Some forms of gingival recession will benefit from soft tissue graft procedure and will be recommended to be done for the subjects whether they are in a study or not as standard of care. All soft tissue grafting surgeries might possess the same surgical risks including; pain, discomfort, bleeding, failure and redo of procedure, swelling, bruising, infection, tooth sensitivity, temporary or permanent numbness in surgical area, inflammation.

Risks related to the anesthetics might include but are not limited to allergic reactions, accidental swallowing of foreign matter, facial swelling or bruising, pain, soreness or discoloration at the site of injection of the anesthetics.

Finally, Breach of confidentiality is always a risk for identifiable subject data.

21.2 Describe procedures performed to lessen the probability or magnitude of risks, including procedures being performed to monitor subjects for safety.

Response:

Review of medical history and medications of the patient, patients will be instructed to use over the counter pain medications including ibuprofen and/or acetaminophen as needed. Also, maintenance of good oral hygiene will decrease the chance of infection or inflammation of the surgical site. Day one and 2 weeks follow-up will be performed and a patient's condition checklist will be followed. Also, the patients will record their pain throughout the first 3 weeks after the surgery.

*21.3 If applicable, indicate **which procedures** may have risks to the subjects that are currently unforeseeable.*

Response:

All soft tissue surgeries will have similar risks whether in the study or outside the study.

21.4 If applicable, indicate which research procedures may have risks to an embryo or fetus should the subject be or become pregnant.

Response:

Upon pregnancy the subject will be withdrawn from the study.

21.5 If applicable, describe risks to others who are not subjects.

Response:

None

22.0 Potential Benefits to Subjects

22.1 Describe the potential benefits that individual subjects may experience by taking part in the research. Include the probability, magnitude, and duration of the potential benefits. Indicate if there is no direct benefit.

NOTE: Compensation **cannot** be stated as a benefit.

Response:

Possible benefits include covering the exposed roots and increase the amount of gingival tissue covering the tooth to help prevent further gingival recession, to maintain oral health, improve tooth prognosis, and help decrease tooth sensitivity and improve esthetics. This research will also help Periodontist make a sound decision on which technique carries the most successful results, the best course of healing, with the least amount of pain and post-operative discomfort, which will help other patients choose the most comfortable procedure for them in the future.

23.0 Compensation for Research-Related Injury

- N/A: The research procedures for this study do not present risk of research related injury (e.g. survey studies, records review studies). This section does not apply.

23.1 *If the research procedures carry a risk of research related injury, describe the available compensation to subjects in the event that such injury should occur.*

Response:

The subjects will get medical treatment if they are injured as a result of taking part in this study. The study doctor will explain the treatment options and tell the subject where they can get treatment.

However, the sponsor will pay for the reasonable costs of medical care for any physical injury that specifically results from the study, to the extent that:

- The injury resulted from the study and not from a pre-existing medical condition
- The costs are not paid for by the subject's medical insurance or other third party
- The injury did not result from a failure to follow study protocol or instructions, or from the negligence or misconduct of the study personnel

23.2 *Provide a copy of contract language, if any, relevant to compensation for research related injury.*

NOTE: *If the contract is not yet approved at the time of this submission, submit the current version here. If the contract is later approved with **different language regarding research related injury**, you must modify your response here and submit an amendment to the IRB for review and approval.*

Response:

Should any Study subject suffer a Protocol-induced injury, Sponsor will pay for reasonable and necessary costs of diagnosis, therapy and/or medical treatment including

hospitalization costs (“Treatment Costs”) for such Protocol-induced injuries. Sponsor will reimburse Institution and/or subjects for such Treatment Costs dependent upon by whom the Treatment Costs were incurred. Sponsor will not be responsible for paying for Treatment Costs associated with the treatment of normal progression of the subject’s disease, nor for injuries resulting from interventions that the subjects would have incurred had they not participated in the Study. Additionally Sponsor will not be responsible for Treatment Costs to the extent such Protocol-induced injury is caused by the malpractice, negligence, error or omission (“Negligence”) by the Investigator, Study Staff or Institution, except to the extent such Negligence is caused by Sponsor or Sponsor’s employees, agents or affiliates. The obligation of Sponsor under this section shall survive termination of this Agreement.

24.0 Economic Burden to Subjects

24.1 Describe any costs that subjects may be responsible for because of participation in the research.

NOTE: Some examples include transportation or parking.

Response:

The treatment will be provided at no cost, but the subjects will not be compensated for their time and their transportation method.

N/A: This study is not enrolling subjects, or is limited to records review procedures only. This section does not apply.

25.0 Compensation for Participation

25.1 Describe the amount and timing of any compensation to subjects, including monetary, course credit, or gift card compensation.

Response:

The subjects will receive all the treatment at no cost.

N/A: This study is not enrolling subjects, or is limited to records review procedures only. This section does not apply.

N/A: There is no compensation for participation. This section does not apply.

26.0 Consent Process

26.1 Indicate whether you will be obtaining consent.

NOTE: This does not refer to consent documentation, but rather whether you will be obtaining permission from subjects to participate in a research study. Consent documentation is addressed in Section 27.0.

Yes (If yes, Provide responses to each question in this Section)

No (If no, Skip to Section 27.0)

26.2 Describe where the consent process will take place. Include steps to maximize subjects’ privacy.

Response:

In the periodontal clinic which is a private quiet room with no one present other than the principle investigator or research assistant or dental assistant. The study details, time involvement, adverse events, and benefits will be explained to the patients, and all their questions will be addressed. The patients will be given at least one week to decide if they want to enroll in the study, if needed.

26.3 *Describe how you will ensure that subjects are provided with a sufficient period of time to consider taking part in the research study.*

NOTE: It is always a requirement that a prospective subject is given sufficient time to have their questions answered and consider their participation. See "SOP: Informed Consent Process for Research (HRP-090)" Sections 5.5 and 5.6.

Response:

The patients will be given at least one week to decide if they want to enroll in the study, if needed.

26.4 *Describe any process to ensure ongoing consent, defined as a subject's willingness to continue participation for the duration of the research study.*

Response:

The patient will be provided a copy of the consent for their reference and records. The consent at the beginning of each visit will be reviewed with the patient to ensure the patient still agrees to receive the treatment before performing any procedure.

26.5 *Indicate whether you will be following "SOP: Informed Consent Process for Research (HRP-090)." If not, or if there are any exceptions or additional details to what is covered in the SOP, describe:*

- *The role of the individuals listed in the application who are involved in the consent process*
- *The time that will be devoted to the consent discussion*
- *Steps that will be taken to minimize the possibility of coercion or undue influence*
- *Steps that will be taken to ensure the subjects' understanding*

Response:

We have reviewed and will be following "SOP: Informed Consent Process for Research (HRP-090)."

Non-English Speaking Subjects

N/A: This study will not enroll Non-English speaking subjects.
(Skip to Section 26.8)

26.6 *Indicate which language(s) other than English are likely to be spoken/understood by your prospective study population or their legally authorized representatives.*

NOTE: The response to this Section should correspond with your response to Section 6.4 of this protocol.

Response:

26.7 *If subjects who do not speak English will be enrolled, describe the process to ensure that the oral and written information provided to those subjects will be in that language. Indicate the language that will be used by those obtaining consent.*

NOTE: Guidance is provided on “SOP: Informed Consent Process for Research (HRP-090).”

Response:

Cognitively Impaired Adults

N/A: This study will not enroll cognitively impaired adults.
(Skip to Section 26.9)

26.8 *Describe the process to determine whether an individual is capable of consent.*

Response:

Adults Unable to Consent

N/A: This study will not enroll adults unable to consent.
(Skip to Section 26.13)

When a person is not capable of consent due to cognitive impairment, a legally authorized representative should be used to provide consent (Sections 26.9 and 26.10) and, where possible, assent of the individual should also be solicited (Sections 26.11 and 26.12).

26.9 *Describe how you will identify a Legally Authorized Representative (LAR). Indicate that you have reviewed the “SOP: Legally Authorized Representatives, Children, and Guardians (HRP-013)” for research in New York State.*

NOTE: Examples of acceptable response includes: verifying the electronic medical record to determine if an LAR is recorded.

Response:

- We have reviewed and will be following “SOP: Legally Authorized Representatives, Children, and Guardians (HRP-013).”

26.10 For research conducted outside of New York State, provide information that describes which individuals are authorized under applicable law to consent on behalf of a prospective subject to their participation in the research. One method of obtaining this information is to have a legal counsel or authority review your protocol along with the definition of “legally authorized representative” in “SOP: Legally Authorized Representatives, Children, and Guardians (HRP-013).”

Response:

26.11 Describe the process for *assent of the adults*:

- *Indicate whether assent will be obtained from all, some, or none of the subjects. If some, indicate which adults will be required to assent and which will not.*

Response:

- *If assent will not be obtained from some or all subjects, provide an explanation of why not.*

Response:

26.12 Describe whether *assent of the adult* subjects will be documented and the process to document assent.

NOTE: The IRB allows the person obtaining assent to document assent on the consent document using the “Template Consent Document (HRP-502)” Signature Block for Assent of Adults who are Legally Unable to Consent.

Response:

Subjects who are not yet Adults (Infants, Children, and Teenagers)

- N/A: This study will not enroll subjects who are not yet adults. (Skip to Section 27.0)**

26.13 Describe the criteria that will be used to determine **whether a prospective subject has not attained the legal age for consent to treatments or procedures involved in the research** under the applicable law of the jurisdiction in which the research will be conducted (**e.g., individuals under the age of 18 years**). For research conducted in NYS, review “SOP: Legally Authorized Representatives, Children, and Guardians (HRP-013)” to be aware of which individuals in the state meet the definition of “children.”

NOTE: Examples of acceptable responses include: verification via electronic medical record, driver’s license or state-issued ID, screening questionnaire.

Response:

26.14 **For research conducted outside of New York State**, provide information that describes which persons have not attained the legal age for consent to treatments or procedures involved the research, under the applicable law of the jurisdiction in which research will be conducted. One method of obtaining this information is to have a legal counsel or authority review your protocol along the definition of “children” in “SOP: Legally Authorized Representatives, Children, and Guardians (HRP-013).”

Response:

26.15 Describe whether parental permission will be obtained from:

Response:

- One parent even if the other parent is alive, known, competent, reasonably available, and shares legal responsibility for the care and custody of the child.
- Both parents unless one parent is deceased, unknown, incompetent, or not reasonably available, or when only one parent has legal responsibility for the care and custody of the child.
- Parent permission will not be obtained. A waiver of parent permission is being requested.

NOTE: The requirement for parent permission is a protocol-specific determination made by the IRB based on the risk level of the research. For guidance, review the “CHECKLIST: Children (HRP-416).”

26.16 Describe whether permission will be obtained from individuals **other than parents**, and if so, who will be allowed to provide permission. Describe your procedure for determining an individual’s authority to consent to the child’s general medical care.

Response:

26.17 Indicate whether assent will be obtained from all, some, or none of the **children**. If assent will be obtained from some children, indicate which children will be required to assent.

Response:

26.18 When assent of children is obtained, describe how it will be documented.

Response:

